## 2.0 Introduction

According to the Centers for Disease Control and Prevention, between 2011 and 2014, 10.7% of Americans reported taking at least one antidepressant in the past month. [1] Antidepressants were the third most commonly used medication after cholesterol and pain medications.

Antidepressants are prescribed for the management of depression, anxiety, and other conditions. Given that the time from initiation of pharmacologic treatment to clinical effect takes two to four weeks,[2, 3] coupled with the fact that the initial medication may not be effective, thus necessitating adjustments to dosages or medications, treatment with an antidepressant can be a long and complicated process, during which patients still experience symptoms.

Strategies to improve treatment often include switching patients to a different antidepressant or prescribing an additional antidepressant.[4]

One reason for poor response to antidepressants can be attributed to the drug metabolism process. Many of the most commonly prescribed antidepressants undergo phase one xenobiotic metabolism by a class of enzymes in the P450 superfamily. This family of enzymes exhibits a high degree of genetic polymorphism, resulting in variable metabolism. Because of this variation in P450, we can classify individuals as poor, intermediate, extensive, and ultra-rapid metabolizers. The consequence of this population heterogeneity is that medications are metabolized at different rates and plasma concentrations of specific drugs can be outside of the optimal range, which may result in adverse drug events or lack of therapeutic effect. Because of these two medication outcomes, treatment may be discontinued.

Pharmacogenomic (PGx) testing of several cytochrome P450 genes and the most frequently described functional variants (CYP2D6, CYP2C9, CYP2C19, and CYP1A2) can be used to predict the metabolic capacity of an individual. For example, it is estimated that 5-10% of Caucasian individuals are poor metabolizers and 1-2% are ultra-rapid metabolizers based on CYP2D6 phenotypes.[5] By knowing a patient's genetic information and the drug's major metabolic pathway, we can prospectively assess the appropriateness of specific medications, modifying the dosing or using enhanced monitoring. By identifying the approximately 10% of individuals who will not metabolize antidepressants properly via the CYP2D6 pathway, we may be better able to identify effective treatment options and minimize adverse effects.

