## 3.0 Objectives

PGx testing could greatly improve the use of antidepressants by aiding prescribers in identifying proper medications for individual patients; thus potentially improving medication adherence, as well as reducing symptoms and antidepressant side effects.

This pilot study will explore the use of PGx testing in primary care, and is guided by several specific aims:

Specific Aim 1: To determine the effect of PGx testing on the primary outcome of physician treatment decisions, as measured by the change in the proportion of patients who are prescribed medications at baseline that are contraindicated according to the PGx test, compared to the proportion at six-month follow-up.

Specific Aim 2: To determine the effect of PGx testing on secondary outcomes measures of interest, including change in symptoms and severity and medication adherence from baseline to six-month follow-up.

Specific Aim 3: To determine the acceptability of PGx testing in primary care among patients and physicians.

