Patient participants will meet with study staff for consent and baseline data collection at a Michigan Clinical Research Unit (MCRU) in either Domino's Farms or the Cardiovascular Center. Once consent and baseline data collection are complete, participants will have their blood drawn by MCRU laboratory staff. A single 4 mL Lavender top EDTA tube of blood will be drawn. Once the blood draw is complete, study staff will send the sample to Progenity for analysis. After the baseline assessment is complete, patient participants will be randomized equally to either have their test results sent immediately to their participating primary care physicians once available, or to have their test results sent in three months. Randomization will be stratified by physician in ten block units to ensure balance by physician. PharmDs on the research team ([name] and [name]) will be available to consult with physician participants at any time during the study; however, our study PharmDs will meet with each participating physician at least once, when their first patient PGx test results are available to provide general, as well as patient specific education about the PGx test and results. These consultations will help physicians to interpret PGx test results, and may help to guide treatment decisions, if necessary. Study pharmacists or staff will not

provide PGx results to patients; it is up to the patient's physician to provide this information if he/she feels it is appropriate. Likewise, although study pharmacists may make treatment recommendations based on the PGx test results, it is up to the treating physician to decide whether to act on those recommendations. All intervention patient participants will be followed for a total of 6 months, with phone-based follow-up assessments occurring at 3- and 6-months. All control patients will be followed for 9 months, with phone-based follow-up assessments occurring at 3-, 6-, and 9-months. Please see Figure 2 for patient participant study flow.

Figure 1. Physician Participant Study Flow

[figure not shown]
[figure not shown]

Figure 2: Patient Participant Study Flow

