## 5.6 Data Analyses

In this study, we expect to enroll up to 30 physician participants and expect a retention rate of 90-100%. We also expect to enroll about 100 patient participants and expect a retention rate of 80% at the completion of this study.

Data from this study will be analyzed by the study statistician. Survey data will be analyzed using descriptive statistics. Multiple-choice questions will be analyzed using standard quantitative techniques including Chi square and t-test. Open-ended responses will be independently coded using qualitative methods, including any transcripts that result from the recorded survey responses.

Independent sample t-tests will be used to compare outcomes between intervention and control groups at each time point, as well as at similar time points after test results were released to physicians (i.e. baseline for intervention vs. 3 month for control group). Linear mixed models will assess the change in outcomes, as well as whether the change is similar between groups. This will be done by including time, study group, and a time by study group interaction as predictors of each outcome. Time will be considered in two ways, first as the time in study, and secondly as time since test results were released to physicians. In the latter, only data from 3-month to 9-month will be included for the control group, and baseline to 6-month for intervention group, due to timing of test result release. Models will be adjusted for patient demographics.

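### The time-since-release mixed model has no unexposed follow-up, so for symptom outcomes neither its change term nor its time-by-group interaction can be read as the effect of PGx testing

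*Combined protocol and SAP*

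**What the plan says.** Specific Aim 2 (section 3.0) asks for the effect of PGx testing on secondary outcomes, "including change in symptoms and severity and medication adherence from baseline to six-month follow-up".

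Section 5.1 randomises patients equally. Intervention patients "have their test results sent immediately to their participating primary care physicians once available"; the laboratory turnaround is not given. Control results are sent at three months.

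Section 5.6 gives the models two purposes: "Linear mixed models will assess the change in outcomes, as well as whether the change is similar between groups". The terms are the same for every outcome: "This will be done by including time, study group, and a time by study group interaction as predictors of each outcome". Two time scales are planned: "Time will be considered in two ways, first as the time in study, and secondly as time since test results were released to physicians". On the second scale, "only data from 3-month to 9-month will be included for the control group, and baseline to 6-month for intervention group".

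Section 5.6 also plans simple comparisons: "Independent sample t-tests will be used to compare outcomes between intervention and control groups at each time point". It adds t-tests aligned on release, giving intervention baseline against control month 3 as the example. It does not say which analysis is primary, which coefficient estimates the PGx effect, whether time is linear or categorical, or what alpha applies.

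**The concern.** The control arm's first three months are the only assessed follow-up interval in which the physician does not hold the results. The time-since-release model leaves that interval out. What remains is follow-up after release in both arms, so the model has nothing unexposed to compare with.

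The competing explanation is in the protocol. Section 5.4.2 admits patients within 4 weeks of a new prescription, and section 2.0 states that "the time from initiation of pharmacologic treatment to clinical effect takes two to four weeks". Symptoms can be expected to improve without any PGx information, and most of that improvement should fall early. On the release scale, the intervention arm contributes study months 0-6 and the control arm months 3-9. The intervention window holds the early recovery and the control window does not. The change term then mixes recovery with any PGx effect, and the interaction sets an early phase of recovery against a later one.

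At stake is how Aim 2 is reported for the PHQ-8 and GAD-7. Ordinary recovery could be taken for an effect of testing. A difference between recovery phases could equally be taken for a difference between early and delayed release.

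**Working it through.** **No figure to reproduce.** The plan states no alpha, power, SD, effect size or expected recovery.

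**Inputs from the documents.** 100 patients, equal allocation and 80% retention (sections 5.1 and 5.6): 100 / 2 × 0.80 = 40 completers per arm.

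**Assumptions.** Two-sided alpha 0.05; outcome SD 1 at every visit; equal correlation ρ = 0.5 between visits (range 0.3 to 0.7); PGx effect zero; recovery of d SD between months 0 and 3 and none afterwards, with d = 0.2 or 0.5.

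**Standard errors of six-month change on the release scale**
- SD of a patient's change: √(2(1 − ρ)) = 1.0 at ρ = 0.5.
- One arm: 1.0 / √40 = 0.158.
- Average of the two arms: 0.158 / √2 = 0.112.
- Difference between arms (the interaction): 0.158 × √2 = 0.224.

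**Expected values with no PGx effect.** The intervention arm changes by d over months 0-6. The control arm changes by 0 over months 3-9. The arm average is d/2 and the interaction is d.

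**Rejection probability** = Φ(δ/SE − 1.96) + Φ(−δ/SE − 1.96), where δ is the expected value of the term.

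| Term | d = 0.5: δ/SE | Significant | d = 0.2: δ/SE | Significant |
|---|---|---|---|---|
| Arm-averaged change | 0.25/0.112 = 2.24 | 61% | 0.10/0.112 = 0.89 | 15% |
| Intervention-arm change | 0.50/0.158 = 3.16 | 89% | 0.20/0.158 = 1.26 | 24% |
| Interaction | 0.50/0.224 = 2.24 | 61% | 0.20/0.224 = 0.89 | 15% |
| Control-arm change | 0 | 5% | 0 | 5% |

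Simulation of the mixed model (4,000 trials, random intercept, linear time, d = 0.5) gave 59%, 88%, 59% and 5%.

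**Sensitivity at d = 0.5.** With ρ from 0.3 to 0.7, the arm-averaged change and the interaction each run from 47% to 82%. At ρ = 0.5, suppose recovery continues by a further 50% of d in months 3-6 and 25% in months 6-9. Simulation then gives 99.9% for the averaged change, 66% for the control-arm slope and 38% for the interaction.

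**Aligned t-test** (intervention baseline against control month 3). SE = √(2/40) = 0.224, so at d = 0.5 it also rejects in about 61% of trials.

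**Contrasts that keep control months 0-3.** Under the same nulls, over all simulated scenarios, the time-in-study interaction rejected in 2.8-5.6% of trials and the month-3 t-test in 4.2-5.9%.

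**Precision of the month-3 contrast at ρ = 0.5.** With baseline as a covariate, or with the arms' baseline means set equal, SE = √(0.05 × (1 − 0.25)) = 0.194, and power for 0.5 SD is about 73%. As a plain difference in change from baseline, SE = 0.224 and power is about 61%.

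**Time-varying released indicator on all visits.** The arms differ in release status only at month 3. Let D0, D3 and D6 be the arm differences at months 0, 3 and 6.
- Without a group main effect, at ρ = 0.5: estimate = D3 − (D0 + D6)/3; SE = √(0.05/1.5) = 0.183; power for 0.5 SD about 78%.
- With a group main effect: estimate = D3 − (D0 + D6)/2; SE = √(0.05 × 0.5 × 1.5) = 0.194; power about 73%.
- If the true effect is 0.25 SD three months after release and 0.5 SD at six, then D0 = 0, D3 = 0.25 and D6 = 0.50 − 0.25 = 0.25. The form without a group effect returns 0.25 − 0.25/3 = 0.17 SD. The form with one returns 0.25 − 0.125 = 0.125 SD. Both lie below either true value.

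**The case against.** The strongest reply is that the plan already holds the right comparison. The t-tests at each time point include month 3, and the time-in-study model has no stated exclusion of control months 0-3. This stands: the information is lost to one model, not to the plan. What remains is that the plan does not name either as the effect estimate, and it presents the release-aligned analyses without a caveat.

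A reader might infer that section 5.6 declares the change since release to be the PGx effect. It does not. It says only that change, and similarity of change, will be assessed, and it sets no decision rule. Aim 2 is framed from baseline to six months, which is study time. The risk lies in what the text leaves open.

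A reader might also infer that the change will be significant in most trials even if testing does nothing. The documents do not support that. They give no recovery size or correlation. Patients may have had up to 4 weeks of drug before screening, so part of the recovery may precede baseline. The answer also depends on coding: with the control arm as reference, the time coefficient is that arm's slope, which stays near 5% if recovery ends by month 3.

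Nor is leaving out months 0-3 what makes the change significant. On the time-in-study scale, which keeps them, the time term rejects in 96-100% of trials at 0.5 SD recovery. Any within-arm change picks up recovery. The fault is the absence of an exposed-versus-unexposed contrast.

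**Conclusion.** The point holds for symptom outcomes. On the time-since-release scale, neither the change nor the interaction can be read as an effect of PGx testing. This follows from the data window and needs no numerical assumption.

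The size of the problem does rest on assumptions. With 40 completers per arm, ρ = 0.5 and a 0.5 SD recovery complete by month 3, false-positive rates are about 61% (averaged change), 89% (intervention-arm change) and 61% (interaction). At 0.2 SD they are about 15%, 24% and 15%. With no recovery every term sits at about 5%.

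The argument does not clearly extend to adherence, healthcare use or the primary prescribing outcome, where recovery after starting a drug is not the obvious alternative explanation. For a pilot whose other planned analyses contain a valid contrast, this is a matter of naming the right estimate and labelling the rest.

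**What to change.** In section 5.6:

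1. Take the PGx effect on symptoms from the randomised month-3 contrast (intervention released, control not). Estimate it in the time-in-study mixed model with baseline included. Treat study month as categorical so that the contrast can be read directly, and say how baseline enters.
2. Label every time-since-release result as descriptive: change, interaction and aligned t-tests.
3. Optionally, replace the time-since-release model with a secondary model on all visits, with categorical study month and a time-varying released indicator (intervention from month 3, control from month 6). State whether it has a group main effect (SE about 0.183 SD without, 0.194 SD with; power at 0.5 SD about 78% and 73%). State also that it assumes a constant effect after release and is attenuated if the effect grows: about 0.17 SD, in the form without a group effect, when the truth is 0.25 then 0.5 SD.

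The cost is SAP wording and one model specification, with no new visits or data. The effect is read at month 3, while Aim 2 names six months. By month 6 both arms have been released, so a comparison there is of earlier against later release. The text should say so.

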## Abstract

**Background:** Antidepressants are commonly prescribed by primary care providers for treating depression, anxiety, and other conditions. A trial and error approach is typically used to identify effective therapy. Treatment efficacy and safety of many antidepressants can vary based on the presence of certain diseases and metabolism gene types. Pharmacogenomic (PGx) testing provides phenotypic classification of individuals as poor, intermediate, extensive, and ultra-rapid CYP450 metabolizers. This allows more accurate drug selection for efficacy and dosing to minimize toxicity.

**Objective:** To determine the preliminary effectiveness of PGx testing for selection of effective antidepressant, medication adherence, depressive symptoms, and healthcare utilization. To determine acceptability of PGx testing in primary care among patients and providers.

**Methods:** This is a 6-month randomized, wait-listed, controlled pilot trial conducted in 6 department of family medicine (DFM) clinics at the University of Michigan (UM). We will enroll physicians practicing at a UM DFM clinical site who are willing to utilize PGx test results in conjunction with treating patients prescribed certain antidepressants. We will also enroll patients of these DFM physicians who are adults with a new prescription for an antidepressant (within the past 4 weeks) including patients who have switched to a new antidepressant from another antidepressant or have added on a new antidepressant to current antidepressant therapy. Patients are excluded if taking an antidepressant for more than 4 weeks and if they have had PGx testing in the past.

Physician participants will complete a baseline survey to assess demographics, and knowledge, acceptability and utility of PGx testing for this population. At the conclusion of the study, physician participants will complete a semi-structured interview to assess knowledge, satisfaction, feasibility, acceptability, effectiveness, barriers to widespread adoption, and utility of PGx testing.

All patients will complete a baseline, 3-, and 6-month assessment; control patients will have an additional 9-month assessment. Data to be collected include reasons for antidepressant use, depression and anxiety symptoms and severity, functional health status (SF-12), PGx knowledge, work status changes, demographic information, physician and emergency department visits, adverse effects, and medication alterations and adherence.

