### **5.4.2 Patient Participants**

To be included in this pilot trial, participants must:

- Be a patient of a participating physician
- Have a new prescription for a certain antidepressant recorded in MiChart (within the previous 4 weeks prior to screening)
- Be currently taking the new antidepressant
- Be willing to undergo PGx testing via single tube blood draw
- Be at least 18 years old

Participants will be excluded from this pilot trial if they:

- Do not speak English
- Have previously undergone PGx testing
- Are unable to provide their own consent to participate in the study
- Have been taking the new targeted antidepressant for longer than 4 weeks (prior to screening)

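### Section 5.6 makes inefficient use of the baseline scores in the Aim 2 comparisons: the t-tests ignore them, and the mixed model leaves the baseline difference between arms free

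*Combined protocol and SAP*

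**What the plan says.** Specific Aim 2 (Section 3.0) concerns "change in symptoms and severity and medication adherence from baseline to six-month follow-up". Table 2 schedules the PHQ-8, GAD-7, SF-12 and adherence measures at baseline, 3 and 6 months in both arms, and again at 9 months in controls. Section 5.1 places randomisation after the baseline assessment, with equal allocation stratified by physician.

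Section 5.6 plans two kinds of between-arm analysis. The first is simple: "Independent sample t-tests will be used to compare outcomes between intervention and control groups at each time point". The second is a model for change: "Linear mixed models will assess the change in outcomes, as well as whether the change is similar between groups". Its terms are given as follows: "This will be done by including time, study group, and a time by study group interaction as predictors of each outcome". The only adjustment is "Models will be adjusted for patient demographics". The models are to be run on two clocks, time in study and time since results reached the physician. On the second clock, controls start at month 3.

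**The concern.** Because baseline is measured before allocation, any difference between the arms at baseline is chance. An efficient analysis uses that fact, either by conditioning on the baseline score or by giving both arms one baseline mean. Neither planned analysis does.

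- The t-test discards the baseline score, so all stable between-patient variation stays in the error.
- The mixed model includes baseline as a response, but its group main effect lets the arms differ there. The interaction then subtracts the whole observed baseline difference, noise included. When the correlation is modest, this over-corrects.

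Adjusting for demographics does not solve this. With complete data, a covariate that is constant over time and enters only as a main effect cancels out of a difference in change.

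What is at stake is the width of the Aim 2 intervals in a trial expecting about 80 completers. A pilot's intervals are one of its main products, and here they would be wider than the collected data require. There is also a choice between two analyses with different precision, and Section 5.6 does not say which one leads.

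**Working it through.** The plan has no figure to reproduce: it states no power, significance level, effect size, SD or correlation.

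**Inputs from the documents.** About 100 patients with 80% retained (Section 5.6) and equal allocation (Section 5.1) give 100 × 0.80 / 2 = 40 completers per arm. The percentage savings below do not depend on this number.

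**Assumptions.** SD = 1 at both visits, complete data, time handled as separate visits, and baseline-to-follow-up correlation r = 0.3, 0.5 or 0.7. For detectable differences only: two-sided 5% and 80% power, so the multiplier is 1.960 + 0.842 = 2.802.

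**Formulas.** The variance of the between-arm difference is f × 2/n, with n = 40 and

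- t-test at follow-up: f = 1
- difference in change (interaction with a free group effect): f = 2(1 − r)
- baseline as covariate, or common baseline mean: f = 1 − r²

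The saving against change is 1 − (1 − r²)/[2(1 − r)] = (1 − r)/2. The saving against the t-test is r².

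| r | SE t-test | SE change | SE adjusted | saving vs change | saving vs t-test |
|---|---|---|---|---|---|
| 0.3 | √(1 × 0.05) = 0.224 | √(1.4 × 0.05) = 0.265 | √(0.91 × 0.05) = 0.213 | 35% | 9% |
| 0.5 | 0.224 | √(1.0 × 0.05) = 0.224 | √(0.75 × 0.05) = 0.194 | 25% | 25% |
| 0.7 | 0.224 | √(0.6 × 0.05) = 0.173 | √(0.51 × 0.05) = 0.160 | 15% | 49% |

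Multiplying by 2.802, the detectable difference moves from 0.74 to 0.60 SD, from 0.63 to 0.54 SD and from 0.49 to 0.45 SD (change to adjusted). For the t-test it is 0.63 SD throughout. At r = 0.5 the adjusted analysis of 80 patients is worth 80 / 0.75 ≈ 107 patients under either planned analysis.

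Below r = 0.5 the t-test beats the change contrast, and above it the order reverses. The adjusted analysis beats both at every r shown.

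**Check by simulation** (400 replicates, 80 patients, three visits, within-patient correlation 0.5, and an invented prognostic factor of 0.3 SD per step). The empirical SE of the 6-month contrast was 0.226 for the planned model and 0.205 for the common-baseline model. The variance saving is 1 − (0.205/0.226)² = 18%. This agrees in direction with the formula's 25% but is smaller. Each simulated SE carries a relative error of about 1/√(2 × 400) = 3.5%, so the gap is not surprising.

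**The case against.** The strongest reply is that baseline is already in the model. A reader who sees that only demographics are named might infer that the models omit the patient's own baseline score. They do not. Baseline is one of the modelled visits, and the interaction is a change from it. The point that remains is efficiency, and the figures above are already computed against that change contrast.

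A second stronger reading is that treatment line should be adjusted for to gain precision. The Abstract admits first starts, switches and patients who "have added on a new antidepressant to current antidepressant therapy", and Section 2.0 observes: "Strategies to improve treatment often include switching patients to a different antidepressant or prescribing an additional antidepressant". But the documents give neither the mix nor the prognostic strength of these groups. In the simulation, line as a main effect left the SE of the planned contrast unchanged (0.226 to 0.226). If line explained 0%, 2%, 5% or 10% of residual variance, the SE ratio after the cost of two degrees of freedom would be 1.013, 1.003, 0.988 or 0.961, so anything from a slight loss to a gain of about 4%. Table 2 names no such variable, and Section 5.5.2 describes chart extraction for the study period only. The precision argument for line does not stand.

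A third is that entry selects adherent patients ("Be currently taking the new antidepressant"), so a later fall could be mistaken for harm from testing. The criterion sets no adherence threshold, any such fall would be expected in both arms, and Section 5.6 explicitly tests whether change is similar between them. This is speculation.

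It is also fair to say that the trial is a pilot without a stated power target, that these are secondary outcomes, and that r is assumed. All of that stands and limits the weight of the point.

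**Conclusion.** The point holds in a narrow form. For the Aim 2 continuous scores, both planned between-arm analyses are less precise than the collected data allow. The avoidable variance is 15% to 35% against the change contrast and 9% to 49% against the t-test, for r between 0.7 and 0.3 and between 0.3 and 0.7 respectively. These figures rest on equal SDs, complete data and assumed correlations. Randomisation protects the between-arm comparison by time in study, so nothing here shows bias, and the documents do not support reading it that way. The importance is moderate: a cheap gain on secondary outcomes of a pilot.

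The gain applies only to the time-in-study analysis. On the time-since-release clock, controls start at month 3, after randomisation, so equal starting means are no longer guaranteed by design.

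**What to change.** In Section 5.6, for time in study only, analyse the PHQ-8, GAD-7, SF-12 and adherence scores by a mixed model on the follow-up visits, with visit, group, visit-by-group, the baseline score and baseline-by-visit. An alternative is to keep baseline as a response and constrain its mean to be equal across arms. Use this in place of the between-arm t-tests at follow-up visits.

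Report the adjusted between-arm difference separately by visit, because the contrast changes meaning. At 3 months it compares results released with results not released. At 6 months it compares earlier with later release, since control results go out at three months (Section 5.1). Do not apply the common-baseline constraint to the time-since-release model.

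The cost is SAP wording and one or two model degrees of freedom. No new data are needed.
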